**P15-743 (HCV RWE) \_ STATISTICAL ANALYSIS PLAN \_ final 2.0 \_ 02 Feb 2018**

**Effectiveness Analyses**

AbbVie LLC  
P15-743 (HCV RWE)  
**Table 2.1.1.1.1. Percentage for effectiveness endpoints (main analysis)**  
The core population  
Page X of X

| Parameter   | ABBVIE REGIMEN + RBV                  |  | ABBVIE REGIMEN - RBV                  |     | Overall
(N=XXX)
n (%)
95% CI |
|---|---------------------------------------|--|---------------------------------------|-----|---------------------------------------|
|   | 12 weeks
(N=XX)
n (%)
95% CI |  | 12 weeks
(N=XX)
n (%)
95% CI |     |                                       |
| Patients achieving SVR12
(single last HCV RNA <50 IU/mL 12 weeks after the last actual dose
of the ABBVIE REGIMEN)                            | XX (XX.X)
(XX.X - XX.X)            |  | XX (XX.X)
(XX.X - XX.X)            | ... | XX (XX.X)
(XX.X - XX.X)            |
| SVR12 non-response  | XX (XX.X)
(XX.X - XX.X)            |  | XX (XX.X)
(XX.X - XX.X)            | ... | XX (XX.X)
(XX.X - XX.X)            |
| Patients with breakthrough
(defined as at least one documented HCV RNA <50 IU/mL
followed by HCV RNA ≥50 IU/mL during treatment)              | XX (XX.X)
(XX.X - XX.X)            |  | XX (XX.X)
(XX.X - XX.X)            | ... | XX (XX.X)
(XX.X - XX.X)            |
| Failure to suppress
(each measured on-treatment HCV RNA value ≥50 IU/mL)   | XX (XX.X)
(XX.X - XX.X)            |  | XX (XX.X)
(XX.X - XX.X)            | ... | XX (XX.X)
(XX.X - XX.X)            |
| Patients with relapse
(HCV RNA <50 IU/mL at EoT or at the last on-treatment HCV RNA
measurement followed by HCV RNA ≥50 IU/mL post-treatment) | XX (XX.X)
(XX.X - XX.X)            |  | XX (XX.X)
(XX.X - XX.X)            | ... | XX (XX.X)
(XX.X - XX.X)            |
| Patients with missing SVR12 data  | XX (XX.X)
(XX.X - XX.X)            |  | XX (XX.X)
(XX.X - XX.X)            | ... | XX (XX.X)
(XX.X - XX.X)            |
| Patients with premature study drug discontinuation with
no on-treatment virological failure  | XX (XX.X)
(XX.X - XX.X)            |  | XX (XX.X)
(XX.X - XX.X)            | ... | XX (XX.X)
(XX.X - XX.X)            |
| Patients achieving SVR24
(single last HCV RNA <50 IU/mL 24 weeks after the last
actual dose of the ABBVIE REGIMEN)                            | XX (XX.X)
(XX.X - XX.X)            |  | XX (XX.X)
(XX.X - XX.X)            | ... | XX (XX.X)
(XX.X - XX.X)            |
| Patients with virological response
(HCV RNA <50 IU/mL) at EoT  | XX (XX.X)
(XX.X - XX.X)            |  | XX (XX.X)
(XX.X - XX.X)            | ... | XX (XX.X)
(XX.X - XX.X)            |

N: the number of patients in the core population.  
n: number of subjects within a specific category.  
EoT: end of treatment.

CONFIDENTIAL AND PROPRIETARY  
Data MATRIX Ltd.

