analysis groups. Response rates (i.e. SVR12 rate, end of treatment [EoT] response rate, relapse rate, viral breakthrough) will be determined for the various CP analysis groups. The relapse rates will be estimated in patients of the CP analysis groups with EoT response and sufficient HCV RNA measurements post treatment. Viral breakthrough rates will be estimated in all patients of the CP analysis groups, who have at least one undetectable HCV RNA measurement on treatment and at least one on-treatment or EoT measurement thereafter. For all rates specified above 95%-confidence intervals (CIs) will be determined using the Clopper-Pearson method.

Univariate and multiple logistic regression (MLR) methods will be used to investigate the impact of various explanatory covariates (e.g. demographic and disease characteristics, co-morbidities, type of treating institution, and prior treatment for CHC and response outcome in treatment experienced patients) on SVR12. These analyses will be of exploratory nature, data driven, and will be performed for various CP analysis groups since not each covariate might be predictive in each patient group. Furthermore, the fact that treatment regimens will differ in the various patient groups has to be taken into account, when selecting the patient groups for each MLR analysis. Backward selection procedures will be applied to generate the final MLR models which will consider only covariates in the selection procedure with a p-value <0.25 in the corresponding univariate logistic regression analysis. A p-value <0.05 will be used for the covariates to stay in the model in a backward elimination step. Logistic regression methods will also be used to investigate the impact of treatment adherence on SVR12.

All safety variables will be summarized for patients in the SP using descriptive statistical methods stratified by the type of combination treatment and scheduled treatment duration.

Milestones:

Start of Data Collection:	Jan 2016
End of Data Collection:	Aug 2017
Final Report of Study Results:	May 2018

Confidential Information

No use or disclose outside AbbVie is permitted without prior written authorization from AbbVie

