9.7.3.3 Statistical Methods for Analysis of Effectiveness Variables

The simple percentage of patients achieving SVR12 will be calculated and an exact two-sided 95% confidence interval (CI) of the percentage will be computed based on the Clopper-Pearson method.

Corresponding methods will be used for other response rates (EoT response rate, relapse rate, viral breakthrough). The relapse rates will be estimated in patients of the CP analysis groups with EoT response and sufficient HCV RNA measurements post-

treatment. Viral breakthrough rates will be estimated in all patients of the CP analysis groups, who have at least one undetectable HCV RNA measurement on-treatment and at least one on-treatment or EoT measurement thereafter.

Univariate and multiple logistic regression (MLR) methods will be used to investigate the impact of the following explanatory covariates on SVR12:

- Key demographic information
- Mode of CHC infection
- HCV RNA level at baseline
- Most recent stage of liver fibrosis
- HCV genotype and subtype (if available)
- Type of treating institute
- Liver and/or CHC related co-morbidities
- Key clinical chemistry and hematology laboratory variables at baseline
- In treatment experienced patients only:
 - Most recent prior treatment for CHC
 - Outcome of most recent prior CHC treatment

Further details and additional covariates will be specified in the SAP.

These analyses will be of exploratory nature, data driven, and will be repeatedly performed for various CP Analysis Groups, since not each covariate might be predictive in each patient group. Furthermore, the fact that treatment regimens will differ in the various patient groups has to be taken into account, when selecting the patient groups for each MLR analysis. Backward selection procedures will be applied to generate the final MLR models which consider only covariates in the selection procedure with a p-value <0.25 in the corresponding univariate logistic regression analysis. A p-value <0.05 will be used for the covariates to stay in the model in a backward elimination step. Logistic regression methods will also be used to investigate the impact of treatment adherence on SVR12.

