**P15-743 (HCV RWE) \_ STATISTICAL ANALYSIS PLAN \_ Final 2.0 \_ 02 Feb 2018**

---

- relapse (HCV RNA <50 IU/mL at EoT or at the last on-treatment HCV RNA measurement followed by HCV RNA  $\geq$ 50 IU/mL post-treatment);
- premature study drug discontinuation with no on-treatment virologic failure;
- missing SVR12 data;
- the percentage of patients achieving SVR24 (single last HCV RNA <50 IU/mL 24 weeks after the last actual dose of the ABBVIE REGIMEN);
- the percentage of patients with virological response (HCV RNA <50 IU/mL) at EoT.

Due to the fact that in the Russian clinical practice tests for HCV RNA often have limit of detection higher than 50 IU/mL (for example, 60 or 100 IU/mL), additional analysis will be performed. In this case all above mentioned effectiveness endpoints will be analyzed with the following definitions:

- the percentage of patients achieving SVR12 (single last HCV RNA value <50 IU/mL or undetectable/negative 12 weeks after the last actual dose of the ABBVIE REGIMEN);
- the percentage of patients with at least one and each of SVR12 non-response categories:
  - breakthrough (at least one documented HCV RNA value <50 IU/mL or undetectable/negative followed by HCV RNA value  $\geq$ 50 IU/mL or positive during treatment);
  - failure to suppress (each measured on-treatment HCV RNA value  $\geq$ 50 IU/mL or positive);
  - relapse (HCV RNA value <50 IU/mL or undetectable/negative at EoT or at the last on-treatment HCV RNA measurement followed by HCV RNA  $\geq$ 50 IU/mL or positive post-treatment);
  - premature study drug discontinuation with no on-treatment virologic failure;
  - missing SVR12 data and/or none of the above criteria;
- the percentage of patients achieving SVR24 (single last HCV RNA value <50 IU/mL or undetectable/negative 24 weeks after the last actual dose of the ABBVIE REGIMEN);
- the percentage of patients with virological response (HCV RNA value <50 IU/mL or undetectable/negative) at EoT.

Achieving SVR12 and presence of breakthrough, relapse or failure to suppress as well as virological response at EoT will be analyzed using univariate logistic regression for both cases (main and sensitivity analyses). These analyses will be of exploratory nature, data driven, and will be repeatedly performed for various CP analysis groups, since not each covariate might be predictive in each patient group. The following parameters can be included in the univariate models as explanatory variables (fixed effect or covariate):

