### **16 Summary of changes to the Protocol**

The analyses methods in this SAP is fully consistent with the clinical study Protocol. The MLR analysis for the PSP results will not be performed due to lack of main predictor variability (the fact of the PSP usage is always “Yes”).

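### The SAP has no output for relapse and breakthrough on the protocol's at-risk denominators; both appear only as SVR12 non-response categories over the whole analysis population

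*SAP*

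**What the plan says.** **Protocol.** Section 9.7.3.2 lists relapse and breakthrough as secondary endpoints in their own right. It lists them again within the breakdown of SVR12 non-response. The two relapse definitions differ: the stand-alone endpoint requires response at EoT, while the category also accepts response at the last on-treatment measurement.

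Section 9.7.3.3 fixes the denominators of the rates. For relapse: "The relapse rates will be estimated in patients of the CP analysis groups with EoT response and sufficient HCV RNA measurements" after treatment. For breakthrough, patients "who have at least one undetectable HCV RNA measurement on-treatment and at least one on-treatment or EoT measurement thereafter". The abstract repeats both rules; for relapse it reads "The relapse rates will be estimated in patients of the CP analysis groups with EoT response and sufficient HCV RNA measurements post treatment".

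**SAP.** Section 3.2.2 keeps both stand-alone endpoints and gives no denominator. Section 9 carries relapse and breakthrough only as SVR12 non-response categories, with the wider relapse definition. Table 2.1.1.1.1 has one row for each, with n (%) and a 95% CI. Its footnotes give "N: the number of patients in the core population" and "n: number of subjects within a specific category". A row for "Patients with missing SVR12 data" stands in the same table. The layout is repeated for the target population and for the core population with sufficient follow-up data (CPSFU).

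On modelling, section 9 says: "Achieving SVR12 and presence of breakthrough, relapse or failure to suppress as well as virological response at EoT will be analyzed using univariate logistic regression". It states no restriction to patients at risk.

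Section 16 says: "The analyses methods in this SAP is fully consistent with the clinical study Protocol". The only departure it names is the dropped regression for the patient support program.

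**The concern.** A patient who never responded at EoT cannot relapse, and a patient with no post-treatment test cannot be seen to relapse. A patient with no test after first becoming undetectable on treatment cannot be seen to break through. The protocol removes these patients from the two rates. A table with a single N equal to the whole population leaves them in.

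Relapse and breakthrough are named secondary effectiveness endpoints, and readers will set them beside rates from other studies of such regimens. As the SAP stands, the reader gets the share of all patients whose SVR12 failure was classed as relapse or breakthrough. That is a legitimate quantity, but it is not the rate that the protocol defines, and nothing in the SAP tells the reader so.

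**Working it through.** **1. The plan's own figure.** Protocol Table 3 and SAP 4.2 give 84.2% to 94.2% as the exact 95% CI for 90% SVR12 with 158 patients. Clopper-Pearson with x = 0.90 × 158 = 142.2 gives 84.23 to 94.20, width 9.97. The figure reproduces. With the whole number x = 142, it is 84.08 to 94.10. The documents state no expected relapse or breakthrough rate.

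**2. Does any SAP output use the risk sets?**

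| Output | Patients in N | Protocol risk set? |
|---|---|---|
| Table 2.1.1.1.1 | Whole core population, including failure to suppress and missing SVR12 | No |
| Table 2.1.1.1.3 | Core population without missing SVR12 | No: does not condition on EoT response, or on a test after first suppression |
| Target-population and CPSFU repeats | Those populations | No |
| SAP 7.1 default | Patients with non-missing data | No: does not condition on earlier response |

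**3. Direction.** Let E be the events, N the population and R the number at risk, with R ≤ N. Then

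(E/N) / (E/R) = R/N ≤ 1.

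For fixed E, both Clopper-Pearson limits also fall as the denominator rises. This compares denominators only. The table's relapse row can also hold more events than the stand-alone endpoint, because of its wider definition, so the numerator needs aligning too.

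**4. Size for relapse, from the plan's own assumption.** At 90% SVR12, about 142 of 158 patients have a response at least 70 days after treatment. They therefore have a post-treatment test. If EoT is missing, the protocol's backward imputation (9.7.1) counts them as EoT responders. Relapsers are at risk by definition. So, approximately,

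R ≥ 142 + E.

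- Floor on R/N before any relapsers are added: 142/158 = 0.90, so the rate is at most about 10% too low in relative terms.
- With an assumed E = 7: R = 149 and R/N = 149/158 = 0.94.
- Whole population: 7/158 = 4.4% (1.8-8.9).
- Risk set: 7/149 = 4.7% (1.9-9.4).

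The difference is 0.3 percentage points.

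**5. Size for breakthrough.** The share with a test after first suppression cannot be bounded in this way, because SVR12 says nothing about how often a patient was tested on treatment. Protocol 9.7.1 leaves HCV RNA testing to the physician. Illustration with 2 assumed events:

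| Assumed share evaluable | R | Rate on risk set | Rate on N = 158 |
|---|---|---|---|
| 90% | 142 | 1.4% (0.2-5.0) | 1.3% (0.2-4.5) |
| 75% | 118 | 1.7% (0.2-6.0) | 1.3% (0.2-4.5) |
| 50% | 79 | 2.5% (0.3-8.8) | 1.3% (0.2-4.5) |

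**The case against.** **The divisor is inferred.** The effectiveness table defines N but does not write out the percentage, as other shells do. SAP 7.1 defaults to patients with non-missing data, and SAP 7.3 rules out imputation for effectiveness. A patient with no post-treatment test might therefore be treated as missing. This stands as a limit on certainty. But one N per column, n defined as the category count, and a missing-SVR12 row inside the table all point to the whole population. The default would not give the protocol's sets in any case.

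**The whole population is right for the breakdown.** This stands. The existing rows are sound as SVR12 non-response categories. What is missing is the second pair of outputs.

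**Little follow-up loss is likely.** A shell footnote says that the core population and CPSFU hold the same patients, and SAP 6 removes early stoppers from the core population. This supports a small effect for relapse. It does not remove the effect: CPSFU admits patients whose last value is 50 IU/mL or more, and those lost for safety reasons, who need not be at risk. The list of target-population and CPSFU tables also treats the equality as conditional.

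**Stronger readings that the documents do not support.** A reader might infer a relapse rate up to 28% too low, by assuming 90% EoT response and 80% follow-up (0.90 × 0.80 = 0.72). That conflicts with the plan. Even 135 at risk with 7 relapses allows at most 128/158 = 81% SVR12, against the planned 90%. A reader might also infer that the regressions make predictors of lost follow-up look protective. No SAP text says that unobserved patients are coded as non-events, and the logistic shells print their own number of patients analysed. The SAP leaves the point open, which is reason to settle it, not evidence of bias.

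**Conclusion.** The point holds as a gap between the supplied protocol and the SAP. Two secondary endpoints have no output on the risk sets that the protocol specifies, and SAP 16 does not say so.

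For relapse the effect is small: at most about 10% relative, and about 0.3 percentage points in the example. This rests on the planned 90% SVR12 and on the protocol's backward imputation at EoT. It could be larger if SVR12 is lower, or if SAP 7.3 is applied literally and responders without an EoT value fall outside the set. For breakthrough the size is unknown and could reach a factor of two if only half the patients were evaluable; that share is an assumption.

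SVR12 is unaffected. One inference to avoid is that the SAP contradicts its governing protocol. It is written from protocol version 4.0 of 11 July 2017, while the version available is 3.0 (country version 1.0). Whether version 4.0 kept these denominators cannot be checked. If it did not, the SAP should still state the ones it uses.

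**What to change.** In SAP 9 and Tables 2.1.x:

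- Keep the present relapse and breakthrough rows, labelled as the SVR12 non-response breakdown over the whole population.
- Add a relapse-rate row using the EoT definition, with N = patients with EoT response and sufficient post-treatment HCV RNA. The protocol does not define sufficient; state that it means at least one post-treatment value.
- Add a breakthrough-rate row, with N = patients with an undetectable on-treatment value and a later on-treatment or EoT value. State that undetectable is read as HCV RNA <50 IU/mL, to match the endpoint definition.
- Print the risk-set N and the Clopper-Pearson CI for each new row.
- State whether the protocol's backward imputation at EoT applies, since SAP 7.3 excludes imputation.
- Fit the relapse and breakthrough regressions in the same risk sets, so that patients without the needed later test cannot be counted as non-events.
- Correct SAP 16, after checking protocol version 4.0.

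The cost is two derived flags, two added rows per table and some wording. No new data are needed. For the same events, the reported rates will be equal or slightly higher.

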**P15-743 (HCV RWE) \_ STATISTICAL ANALYSIS PLAN \_ final 2.0 \_ 02 Feb 2018**

---

SVR12: sustained virological response at 12 weeks after end of treatment.

SVR24: sustained virological response at 24 weeks after end of treatment.

95% confidence intervals determined using the Clopper-Pearson method.

Table for the core population is the same table for the core population with sufficient follow-up data because the core population and the core population with sufficient follow-up data are equal (contain exactly the same subjects).

[1] 95% confidence intervals determined using the Clopper-Pearson method.

Program code, date, time

Data extracted: DD.MM.YYYY

Similar to table 2.1.1.1, the following table will be constructed:

**Table 2.1.1.1.2. Percentage for effectiveness endpoints (additional analysis)**

**P15-743 (HCV RWE) \_ STATISTICAL ANALYSIS PLAN \_ final 2.0 \_ 02 Feb 2018**

AbbVie LLC  
P15-743 (HCV RWE)  
The core population  
Page X of X

**Table 2.1.1.1.3. Percentage for effectiveness endpoints without patients with missing SVR12 results (main analysis)**

| Parameter   | ABBVIE REGIMEN + RBV                  |  | ABBVIE REGIMEN - RBV                  |     | Overall
(N=XXX)
n (%)
95% CI |
|---|---------------------------------------|--|---------------------------------------|-----|---------------------------------------|
|   | 12 weeks
(N=XX)
n (%)
95% CI |  | 12 weeks
(N=XX)
n (%)
95% CI |     |                                       |
| Patients achieving SVR12
(single last HCV RNA <50 IU/mL 12 weeks after the last actual dose
of the ABBVIE REGIMEN)                            | XX (XX.X)
(XX.X - XX.X)            |  | XX (XX.X)
(XX.X - XX.X)            | ... | XX (XX.X)
(XX.X - XX.X)            |
| SVR12 non-response  | XX (XX.X)
(XX.X - XX.X)            |  | XX (XX.X)
(XX.X - XX.X)            | ... | XX (XX.X)
(XX.X - XX.X)            |
| Patients with breakthrough
(defined as at least one documented HCV RNA <50 IU/mL
followed by HCV RNA ≥50 IU/mL during treatment)              | XX (XX.X)
(XX.X - XX.X)            |  | XX (XX.X)
(XX.X - XX.X)            | ... | XX (XX.X)
(XX.X - XX.X)            |
| Failure to suppress
(each measured on-treatment HCV RNA value ≥50 IU/mL)   | XX (XX.X)
(XX.X - XX.X)            |  | XX (XX.X)
(XX.X - XX.X)            | ... | XX (XX.X)
(XX.X - XX.X)            |
| Patients with relapse
(HCV RNA <50 IU/mL at EoT or at the last on-treatment HCV RNA
measurement followed by HCV RNA ≥50 IU/mL post-treatment) | XX (XX.X)
(XX.X - XX.X)            |  | XX (XX.X)
(XX.X - XX.X)            | ... | XX (XX.X)
(XX.X - XX.X)            |
| Patients with premature study drug discontinuation with
no on-treatment virological failure  | XX (XX.X)
(XX.X - XX.X)            |  | XX (XX.X)
(XX.X - XX.X)            | ... | XX (XX.X)
(XX.X - XX.X)            |
| Patients achieving SVR24
(single last HCV RNA <50 IU/mL 24 weeks after the last
actual dose of the ABBVIE REGIMEN)                            | XX (XX.X)
(XX.X - XX.X)            |  | XX (XX.X)
(XX.X - XX.X)            | ... | XX (XX.X)
(XX.X - XX.X)            |
| Patients with virological response
(HCV RNA <50 IU/mL) at EoT  | XX (XX.X)
(XX.X - XX.X)            |  | XX (XX.X)
(XX.X - XX.X)            | ... | XX (XX.X)
(XX.X - XX.X)            |

N: the number of patients in the core population, n: number of subjects within a specific category, EoT: end of treatment.  
SVR12: sustained virological response at 12 weeks after end of treatment. SVR24: sustained virological response at 24 weeks after end of treatment.  
[1] 95% confidence intervals determined using the Clopper-Pearson method.  
Table for the core population is the same table for the core population with sufficient follow-up data because the core population and the core population with sufficient follow-up data are equal (contain exactly the same subjects).

Program code, date, time

Data extracted: DD.MM.YYYY

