9.7.3.2 Secondary Effectiveness Endpoints

The secondary effectiveness endpoints are:

- The percentage of patients with virological response (HCV RNA <50 IU/mL) at EoT
- The percentage of patients with relapse (defined as HCV RNA <50 IU/mL at EoT followed by HCV RNA ≥50 IU/mL)
- The percentage of patients with breakthrough (defined as at least one documented HCV RNA <50 IU/mL followed by HCV RNA ≥50 IU/mL during treatment).
- The number and percentage of patients meeting each and any of the following SVR12 non-response categories:
 - On-treatment virologic failure (breakthrough [defined as above] or failure to suppress [each measured on-treatment HCV RNA value ≥50 IU/mL])
 - Relapse (defined as HCV RNA <50 IU/mL at EoT or at the last on-treatment HCV RNA measurement followed by HCV RNA ≥50 IU/mL post-treatment)
 - Premature study drug discontinuation with no on-treatment virologic failure
 - Missing SVR12 data and/or none of the above criteria

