P15-743 (HCV RWE)\_ STATISTICAL ANALYSIS PLAN \_ Final 2.0 \_ 02 Feb 2018

The non-core population (NCP) – patients not receiving the treatment recommended in the local label (patients with EoT ≤study day 55 for 12 weeks treatment and patients with EoT ≤study day 139 for 24 weeks treatment).

The core population with sufficient follow-up data (CPSFU) – all CP patients, who fulfil one of the following criteria:

- evaluable HCV RNA data ≥70 days after the last actual dose of the ABBVIE REGIMEN (i.e. data within the SVR12 time window);
- a HCV RNA value ≥50 IU/mL at the last measurement post-baseline (i.e. no virological response achieved at the last measurement on-treatment or post-treatment);
- HCV RNA <50 IU/mL at the last measurement post-baseline, but no HCV RNA measurement ≥70 days after the last actual dose of the ABBVIE REGIMEN due to reasons related to safety (e.g. dropped out due to AE) or incomplete efficacy information (e.g. virologic failure such as relapse is reported in the eCRF but date and value of the corresponding HCV RNA test is missing).

In this way, only patients who had virological response at their last on-treatment or post-treatment measurement, but had no HCV RNA measurements ≥70 days post-treatment for reasons not related to safety or effectiveness (e.g. lost-to-follow-up or patient not willing to perform an additional HCV RNA test ≥70 days post-treatment) will be excluded from this analysis.

Figure 6.1 illustrates the patients selection for CPSFU.

[figure not shown]

Figure 6.1 – The core population with sufficient follow-up data (CPSFU) allocation

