**Table 1.2 The reasons of early withdrawal**  
The target population  
Page X of X

|  | ABBVIE REGIMEN + RBV
12 weeks
(N = XX)
n (%) | ABBVIE REGIMEN - RBV
12 weeks
(N = XX)
n (%) | Overall
(N = XX)
n (%) |
|--|---|---|------------------------------|
| Subjects with HCV RNA assessment performed at least 10 weeks post-treatment (i.e. >= 70 days after EoT)    | XX (XX.X)   | XX (XX.X)   | XX (XX.X)                    |
| Subjects without HCV RNA assessment performed at least 10 weeks post-treatment (i.e. >= 70 days after EoT) | XX (XX.X)   | XX (XX.X)   | XX (XX.X)                    |
| Reason if HCV RNA assessment on SVR12 not done:  |   |   |                              |
| Failure to return  | XX (XX.X)   | XX (XX.X)   | XX (XX.X)                    |
| Insufficient virological response  | XX (XX.X)   | XX (XX.X)   | XX (XX.X)                    |
| Withdrawn consent  | XX (XX.X)   | XX (XX.X)   | XX (XX.X)                    |
| Death  | XX (XX.X)   | XX (XX.X)   | XX (XX.X)                    |
| ....   | ....  | ....  | ....                         |

N: the number of subjects in the target population.

n: the number of subjects within a specific category. Percentages were calculated as (100 x n/N).

Program code, date, time

Data extracted: DD.MM.YYYY

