**P15-743 (HCV RWE)\_ STATISTICAL ANALYSIS PLAN \_ final 2.0 \_ 02 Feb 2018**

Similar to table 2.1.1.3, the following table will be constructed:

Table 2.1.1.4. Percentage for effectiveness endpoints without patients with missing SVR12 (additional analysis)

If the target population and the core population with sufficient follow-up data will not be equal to the core population, the following tables will be presented:

Table 2.1.2.1. Percentage for effectiveness endpoints (main analysis)

The target population

Table 2.1.2.2. Percentage for effectiveness endpoints (additional analysis)

The target population

Table 2.1.2.3. Percentage for effectiveness endpoints without patients with missing SVR12 (main analysis)

The target population

Table 2.1.2.4. Percentage for effectiveness endpoints without patients with missing SVR12 (additional analysis)

The target population

Table 2.1.3.1. Percentage for effectiveness endpoints (main analysis)

The core population with sufficient follow-up data

Table 2.1.3.2. Percentage for effectiveness endpoints (additional analysis)

The core population with sufficient follow-up data

Table 2.1.3.3. Percentage for effectiveness endpoints without patients with missing SVR12 (main analysis)

The core population with sufficient follow-up data

Table 2.1.3.4. Percentage for effectiveness endpoints without patients with missing SVR12 (additional analysis)

The core population with sufficient follow-up data

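### The supplementary tables without missing SVR12 state an exclusion that ignores the reason; read literally, they drop untested failures and safety dropouts that the CPSFU rule keeps

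*SAP*

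**What the plan says.** **The tables.** The SAP shells (section 18) contain Table 2.1.1.1.3, "Percentage for effectiveness endpoints without patients with missing SVR12 results (main analysis", for the CP. Table 2.1.1.4 repeats it for the additional analysis. If the populations differ, Tables 2.1.2.3 and 2.1.2.4 do the same for the TP, and Tables 2.1.3.3 and 2.1.3.4 for the CPSFU: "Table 2.1.3.3. Percentage for effectiveness endpoints without patients with missing SVR12 (main analysis". The titles give no exception by reason. SAP section 9 does not mention these tables. The footnote to Table 2.1.1.1.3 still defines N as the whole core population.

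**Why a test may be missing.** SAP Table 1.2 lists reasons for having no SVR12 assessment. They include "Insufficient virological response" and death, alongside failure to return and withdrawn consent.

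**The CPSFU rule.** SAP section 6 and Protocol 9.7.1 keep three groups:
- patients with evaluable HCV RNA at least 70 days after the last dose;
- patients with "a HCV RNA value ≥50 IU/mL at the last measurement post-baseline" (criterion 2);
- patients whose last value was a response but who have no later test "due to reasons related to safety (e.g. dropped out due to AE) or incomplete efficacy information" (criterion 3).

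The SAP states the consequence: "In this way, only patients who had virological response at their last on-treatment or post-treatment measurement, but had no HCV RNA measurements" at 70 days or later, for reasons unrelated to safety or effectiveness, are left out.

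**The missing category.** Protocol 9.7.3.2 makes it residual: "Missing SVR12 data and/or none of the above criteria". SAP section 9 keeps that wording for the additional analysis, but for the main analysis lists missing SVR12 data on its own.

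**The concern.** Patients can lack an SVR12 test because treatment failed or because of a safety event, and Table 1.2 anticipates this. Take a patient with breakthrough at week 8, or with HCV RNA of 50 IU/mL or more at post-treatment week 4, and no later test. The failure is documented, yet the SVR12 result is missing, so a programmer following the title would remove the patient. The CPSFU rule was written to prevent exactly this: it sets aside "only patients who had virological response at their last on-treatment or post-treatment measurement" and were then lost for unrelated reasons.

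At stake is a table that looks like a follow-up-corrected SVR12 rate but may have lost known failures from its denominator. Observed breakthroughs and early relapses would also disappear from their own rows.

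**Working it through.** **1. The plan's own figure.** SAP 4.2 and Protocol 9.5 give 158 evaluable patients at an SVR12 rate of 90%, with an exact two-sided 95% Clopper-Pearson interval of 84.2% to 94.2%. With x = 0.90 × 158 = 142.2, the calculation returns 84.2% to 94.2%. The sample size is not in dispute.

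**2. Direction.** Let x be the SVR12 achievers, n the denominator and k the non-achievers removed. The rate moves from x/n to x/(n − k). A patient without an SVR12 result cannot be in x, so the rate can only rise.

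**3. Who is removed under each reading of the title.**

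| Patient without an SVR12 result | CPSFU rule | Title read literally |
|---|---|---|
| Last value a response, lost for unrelated reasons | excluded | removed |
| Last value ≥50 IU/mL, no later test | kept (criterion 2) | removed |
| Last value a response, test missing for safety reasons or incomplete efficacy information | kept (criterion 3) | removed |

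In Table 2.1.3.3 the first row is already empty. The only patients left to remove are those in rows two and three, plus any tested only after day 112. That last group arises because CPSFU criterion 1 has no upper day limit, whereas the SAP's SVR12 window (Table 5.1) closes at day 112. If the CP and CPSFU contain the same subjects, as the footnote to Table 2.1.1.1.3 says, the same holds for that table.

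**4. Size per patient.** From the planned 158 with 142 achievers: 142/158 = 89.9% and 142/157 = 90.4%, a gain of about 0.6 points. From a CPSFU of 150 with 140 achievers: 140/150 = 93.3% and 140/149 = 94.0%, a gain of 0.6. Near the end of the range, 140/145 = 96.6% and 140/144 = 97.2%, a gain of 0.7.

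**5. Illustration (the split is assumed).** Take 158 CP patients: 140 SVR12, 10 documented failures, and 8 last-value responders lost for unrelated reasons. The CP rate is 140/158 = 88.6%. The CPSFU rate is 140/(158 − 8) = 140/150.

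| Untested failures dropped | Rate | 95% CI |
|---|---|---|
| 0 (CPSFU rule) | 140/150 = 93.3% | 88.1 to 96.8 |
| 2 | 140/148 = 94.6% | 89.6 to 97.6 |
| 4 | 140/146 = 95.9% | 91.3 to 98.5 |
| 6 | 140/144 = 97.2% | 93.0 to 99.2 |
| 10 (bound) | 140/140 = 100% | 97.4 to 100 |

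A second assumed split (142 SVR12, 10 failures, 6 unrelated losses) behaves the same way: 142/152 = 93.4% under the CPSFU rule, then 94.7%, 95.9% and 97.3% with 2, 4 and 6 dropped.

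**The case against.** The strongest reply is that the SAP never says documented failures are dropped; the phrase is simply undefined. The Protocol treats missing as residual, the shell deletes only the missing-data row, and it keeps rows for breakthrough, failure to suppress, relapse and premature discontinuation. The N footnote still names the whole core population. If only residual-missing patients leave, no documented failure is lost.

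This ambiguity stands, but it does not clear the tables. The SAP main analysis has dropped the residual wording, and tested patients can fill the retained rows. Under the residual reading, Table 2.1.3.3 would remove almost nobody. Under the footnote read literally, nobody is removed and the title is wrong. Each reading leaves something to correct.

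Several stronger inferences are not supported:
- **That the CPSFU rule is undone.** Its definition is intact, and Table 2.1.3.1 reports it without this exclusion when the CPSFU differs from the CP.
- **That the primary result is inflated.** Table 2.1.1.1.1 keeps the full CP and lists missing SVR12 under non-response.
- **That only failures are removed.** Last-value responders lost to follow-up also leave the CP and TP tables, and patients tested only after day 112 may leave the CPSFU table.
- **That this is an undeclared departure from the protocol.** The SAP follows Protocol version 4.0, and the protocol available is version 3.0, so this cannot be checked.

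The SAP's CP also already excludes patients whose treatment ended by day 55 (12-week regimen) or day 139 (24-week regimen). Many early failures and safety dropouts therefore never reach the CP or CPSFU tables; the TP tables are more exposed.

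**Conclusion.** The point holds for the supplementary tables only. Their titles state an exclusion that takes no account of reason, and section 9 does not define it. Applied literally, it removes the untested failures and safety dropouts that CPSFU criteria 2 and 3 keep, and it moves SVR12 in one direction only. Table 2.1.3.3 is the clearest case.

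The size cannot be fixed from the documents, which give no count of untested failures. The per-patient effect of 0.6 to 0.7 points rests on about 90% to 97% SVR12 with roughly 144 to 158 patients. The rise from 93.3% to between 94.6% and 97.2% rests on the assumed split and on 2 to 6 dropped failures. The 100% figure is a bound that requires every failure to be untested, not an expectation. If the SAP intends only residual-missing patients to leave, the effect is nil, but the text has to say so.

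**What to change.** In SAP section 9 and the shells:

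1. Limit the exclusion to patients whose last post-baseline HCV RNA was a response and whose SVR12 test is missing for reasons unrelated to safety or effectiveness.
2. Keep documented breakthrough, failure to suppress, relapse and safety-related dropouts in the denominator as SVR12 non-response.
3. Change the N footnote to the reduced denominator, and report the number removed by reason.
4. Drop Tables 2.1.3.3 and 2.1.3.4, which then duplicate 2.1.3.1 and 2.1.3.2.

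Deleting the CP and TP versions as well is not needed.

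The cost is wording and shell edits, with no new data. The SVR12 rate in these tables will be slightly less favourable than under the literal title, and the CP version will largely match the CPSFU result.
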